### **2.3 Study Rationale**

LYR-210 has undergone non-clinical safety assessments to demonstrate suitability for human study. A summary of non-clinical studies of LYR-210 is provided in Investigator Brochure (IB, Section 4.2). LYR-210 (2500 µg) was assessed in a multi-centered, prospective, open-label, single-arm study (clinicaltrials.gov ID: NCT02967731) in 20 adult CS subjects who had failed

previous medical management and have not undergone ESS. A summary of this Phase I study is provided in IB (Section 5).

The Phase I study concluded that LYR-210 (2500 µg) is safe and well-tolerated in ESS-naïve CS subjects and leads to sustained symptom improvement, measured by a CS disease specific 22-item sino-nasal outcome test (SNOT-22) questionnaire , in subjects. These initial clinical experiences with LYR-210 (2500 µg) in CS subjects suggest encouraging clinical benefits without the need for surgery, while avoiding safety risks associated with prolonged oral steroid treatment. The main limitations in the Phase I study, however, include the small sample size and lack of a concurrent control group. Therefore, the potential contribution of a placebo effect is unknown. A larger clinical study which is randomized and blinded to a control will reduce the potential for treatment and assessment bias and will improve the veracity of detected safety and efficacy, particularly in the use of self-reported ePRO instruments for assessment of CS symptoms.

Additionally, CS subject symptom severity can be stratified with being “normal” defined on the SNOT-22 score as <8, “Mild” as 8-20 inclusive, “moderate” as >20-50 and “severe” as >50 . After 24 weeks of treatment with LYR-210 (2500 µg), although 20% subject had achieved optimal “normal” symptom scores, some remained symptomatic (data on file with Lyra Therapeutics). These results indicate room for further symptom reduction in more subjects, possibly with more optimal drug dosing.

Lyra Therapeutics is conducting a global, multicenter study in a randomized, sham procedure-controlled, parallel-group, subject-blinded fashion in approximately 70 adults CS subjects who have failed previous medical management and have not undergone ESS. Subjects enrolled in the study will include patients who have not had ESS but their symptoms are not adequately controlled on medical management and are seeking further treatment. This may include patients who are considering sinus surgery or those who have decided against it. The efficacy and safety of LYR-210 (2500 µg) and LYR-210 (7500 µg) versus a sham procedure control will be assessed. Additionally, LYR-210 (2500 µg) and LYR-210 (7500 µg) will be compared to evaluate dose related responses.

### 3. STUDY OBJECTIVES AND ENDPOINTS

The study objectives and endpoints are:

Study Objectives	Endpoints
Primary	
To evaluate the efficacy of LYR-210 in improving the composite score of 7-day average scores of 4 CS cardinal symptoms (CS7DA4S) at Week 4	
 
- Change from baseline (CFBL) in CS7DA4S score at Week 4
 
 
The 4 CS cardinal symptoms include nasal blockage/obstruction/congestion, facial pain/pressure, reduction/loss of sense of smell, and anterior/posterior nasal discharge. Each symptom is scored on a 0-3 scale as follows: 0 = none, 1 = mild, 2 = moderate, and 3 = severe.

Key Secondary	
To evaluate the efficacy of LYR-210 in improving CS7DA4S score at end of treatment	
 
- CFBL in CS7DA4S score at Week 24
 

To evaluate the effect of LYR-210 in reducing sinus inflammation as per magnetic resonance imaging (MRI)	
 
- Percentage of subjects with at least 1-point decrease in the bilateral Zinreich score in at least 1 pair of the anterior ethmoid, maxillary, posterior ethmoid, frontal, or sphenoid sinuses at Week 24
 
 
Each sinus is scored on a 0-5 scale per the Zinreich modified Lund-Mackay scoring system and based on the percentage of opacification as follows: 0 = 0%, 1 = 1% to 25%, 2 = 26% to 50%, 3 = 51% to 75%, 4 = 76 % to 99%, and 5 = 100% or completely occluded.

To evaluate the time to treatment failure	
 
- Time to treatment failure
 
 
A treatment failure is defined as, after subject enrollment, subject being recommended by treating physician for oral corticosteroid or ESS due to worsening of CS symptoms, or the subject complaint of persistent CS symptoms with an average CS7DA4S score over the preceding 30 days greater than or equal to the Baseline CS7DA4S score.

Other Secondary	


To evaluate the safety and tolerability of LYR-210
	
 
- Severity and percentage of subjects reporting treatment-emergent adverse events (TEAEs) and serious adverse events (TESAEs) through Weeks 2, 4, 12, and 24
 
- Severity and percentage of subjects reporting Day 1 administration procedure and Week 24 removal procedure related AEs and SAEs
 
- Severity and percentage of subjects reporting product related AEs and SAEs on Day 1 and through Weeks 2, 4, 12, and 24
 
- Percentage of subjects with clinically significant abnormal and clinically significant abnormal laboratory values (hematology and chemistry, vital signs) on Day 1 and at Weeks 4, 12, and 24
 
- Morning serum cortisol levels on Day 1 and at Weeks 4, 12, and 24
 
- Severity and percentage of subjects with adverse nasal endoscopic findings and adverse nasal endoscopic findings requiring medical treatment in one or both nostrils on Day 1 and at Weeks 2, 4, 12, and 24
 
- Percentage of subjects with elevated intraocular pressure (IOP) in one or both eyes at Weeks 4, 12, and 24
 
- Percentage of subjects with a clinically significant increase of IOP at Weeks 4, 12, and 24
 
 
A clinically significant increase of IOP is defined as IOP in one or both eyes > 28 mmHg or an increase of IOP from Baseline in one or both eyes <math>\geq</math> 10 mmHg.
 
 
- Percentage of subjects with newly identified or worsened cataract in one or both eyes by slit-lamp examination at Week 24
 

To evaluate the time to onset of action of LYR-210
	
 
- Time to onset of action
 
 
Time to onset of action is defined as, within the first 30 days, the time when all subsequent mean CFBL in the CS7DA4S score of the LYR-210 is statistically significantly greater than that for the sham procedure.

To evaluate the efficacy of LYR-210 in improving CS7DA4S score and the 7-day average score of each of the 4 cardinal CS symptoms
	
 
- CFBL in the CS7DA4S score at Weeks 8, 12, 16, and 20
 
- CFBL in 7-day average score of nasal blockage/obstruction/congestion, reduction/loss of sense of smell, facial pain/pressure, and anterior/posterior nasal discharge at Weeks 1, 2, 3, 4, 8, 12, 16, 20, and 24
 


To evaluate the effect of LYR-210 in improving CS disease-specific quality of life as per 22-item sino-nasal outcome test (SNOT-22) questionnaire
	
 
- CFBL in total SNOT-22 score and SNOT-22 rhinologic, extra-nasal rhinologic, ear-facial, sleep dysfunction, and psychological subdomain scores at Weeks 2, 4, 8, 12, 16, 20, and 24
 

To evaluate the effect of LYR-210 in reducing sinus inflammation as per magnetic resonance imaging (MRI)
	
 
- CFBL in bilateral Zinreich scores of posterior ethmoid, frontal, sphenoid, maxillary, anterior ethmoid sinus and OMC pairs at Week 24
 
- CFBL in total Zinreich score at Week 24
 

To evaluate the effect of LYR-210 in reducing subjects' needs for medical or surgical treatment for CS
	
 
- Percentage of subjects with use of oral antibiotics for CS through Weeks 4, 8, 12, 16, 20, and 24
 
- Percentage of subjects with use of oral corticosteroid for CS through Weeks 4, 8, 12, 16, 20, and 24
 
- Percentage of subjects with use of intranasal corticosteroid sprays for CS through Weeks 4, 8, 12, 16, 20, and 24
 
- Percentage of subjects being recommended by treating physician for ESS through Weeks 4, 8, 12, 16, 20, and 24
 

To evaluate the pharmacokinetics of LYR-210
	
 
- Plasma MF concentrations at [REDACTED] 4, 12, 24
 
 
[REDACTED]

To evaluate the effect of LYR-210 in improving subjects' general quality of life as per 36-item short form health survey version 2 (SF-36v2) questionnaire
	
 
- CFBL in SF-36v2 physical health, mental health, and domain scores at Week 24
 

To evaluate LYR-210 in improving smell function assessed by the University of Pennsylvania Smell Identification Test (UPSIT™)
	
 
- CFBL in UPSIT score at Week 24
 

Exploratory
	

To evaluate the percentage of subjects experiencing acute exacerbations of CS (AECS)
	
 
- Percentage of subjects experiencing AECS through Weeks 4, 8, 12, 16, 20, and 24
 
 
AECS is defined as a sudden worsening of symptoms in a subject resulting in the treating physician reporting an escalation of treatment.


To assess effect of LYR-210 in reducing polyp severity within middle meatus in subgroup of CS subjects with nasal polyps (CSwNP)
	
 
- Percentage of subjects with improvement from Baseline in nasal polyp severity within middle meatus in CSwNP subjects at Week 24
 

To assess efficacy of LYR-210 in improving CS7DA4S score, the 7-day average score of each of 4 CS cardinal symptoms, the SNOT-22 total and subdomain scores, and the SF-36v2 physical health, mental health, and domain scores in the subgroups of CS subjects without nasal polyps (CSsNP) and CSwNP subjects
	
 
- CFBL in the CS7DA4S score at Weeks 1, 2, 3, 4, 8, 12, 16, 20, and 24
 
- CFBL in 7-day average score of nasal blockage/obstruction/congestion, reduction/loss of sense of smell, facial pain/pressure, anterior/posterior nasal discharge in CSsNP and CSwNP subjects at Weeks 1, 2, 3, 4, 8, 12, 16, 20, and 24
 
- CFBL in total SNOT-22 score and SNOT-22 rhinologic, extra-nasal rhinologic, ear-facial, sleep dysfunction, and psychological subdomain scores in CSsNP and CSwNP subjects at Weeks 2, 4, 8, 12, 16, 20, and 24
 
- CFBL in SF-36v2 physical health, mental health, and each of the health domain scores in CSsNP and CSwNP subjects at Week 24
 

To assess efficacy of LYR-210 in reducing sinus inflammation in CSsNP and CSwNP subjects
	
 
- Percentage of subjects with at least 1 point of decrease in the bilateral Zinreich score in at least 1 pair of the posterior ethmoid, frontal, or sphenoid sinuses in CSsNP and CSwNP subjects at Week 24
 

	
 
- CFBL in bilateral Zinreich scores of posterior ethmoid, frontal, sphenoid, maxillary, anterior ethmoid sinus, and OMC pairs in CSsNP and CSwNP subjects at Week 24
 
- CFBL in total Zinreich score at in CSsNP and CSwNP subjects Week 24
 

To assess effect of LYR-210 in improving smell function in CSsNP and CSwNP subjects	
 
- CFBL in UPSIT score in CSsNP and CSwNP subjects at Week 24
 

To assess the safety of subjects post LYR-210 treatment	
 
- Severity and percentage of subjects reporting AEs and SAEs through Week 28 and Week 48
 
- Percentage of subjects with abnormal and clinically significant abnormal laboratory values (hematology and chemistry, vital signs) at Week 28
 
- Morning serum cortisol levels at Week 28
 
- Plasma MF concentration at Week 28
 
- Severity and percentage of subjects with adverse nasal endoscopic findings and adverse nasal endoscopic findings requiring medical treatment in one or both nostrils at Week 28
 
- Percentage of subjects with elevated IOP in one or both eyes at Week 48
 
- Percentage of subjects with a clinically significant increase of IOP at Week 48
 
- Percentage of subjects with newly identified or worsened cataract in one or both eyes by slit-lamp examination at Week 48
 

To assess the durability of efficacy post LYR-210 treatment	
 
- Percentage of subjects with improvement from Baseline in nasal polyp severity within middle meatus in CSwNP subjects at Week 28
 
- CFBL in the CS7DA4S score at Weeks 28, 32, 36, 40, 44, and 48
 
- CFBL in 7-day average score of nasal blockage/obstruction/congestion, reduction/loss of sense of smell, facial pain/pressure, anterior/posterior nasal
 

	
discharge in CSsNP and CSwNP subjects at Weeks 28, 32, 36, 40, 44, and 48
 

- CFBL in total SNOT-22 score and SNOT-22 rhinologic, extra-nasal rhinologic, ear-facial, sleep dysfunction, and psychological subdomain scores at Weeks 28, 32, 36, 40, 44, and 48

- CFBL in SF-36v2 physical health, mental health, and each of the health domain scores at Week 48

--	--

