
To assess efficacy of LYR-210 in improving CS7DA4S score, the 7-day average score of each of 4 CS cardinal symptoms, the SNOT-22 total and subdomain scores, and the SF-36v2 physical health, mental health, and domain scores in the subgroups of CS subjects without nasal polyps (CSsNP) and CSwNP subjects
	
 
- CFBL in the CS7DA4S score at Weeks 1, 2, 3, 4, 8, 12, 16, 20, and 24
 
- CFBL in 7-day average score of nasal blockage/obstruction/congestion, reduction/loss of sense of smell, facial pain/pressure, anterior/posterior nasal discharge in CSsNP and CSwNP subjects at Weeks 1, 2, 3, 4, 8, 12, 16, 20, and 24
 
- CFBL in total SNOT-22 score and SNOT-22 rhinologic, extra-nasal rhinologic, ear-facial, sleep dysfunction, and psychological subdomain scores in CSsNP and CSwNP subjects at Weeks 2, 4, 8, 12, 16, 20, and 24
 
- CFBL in SF-36v2 physical health, mental health, and each of the health domain scores in CSsNP and CSwNP subjects at Week 24
 

To assess efficacy of LYR-210 in reducing sinus inflammation in CSsNP and CSwNP subjects
	
 
- Percentage of subjects with at least 1-point decrease in the bilateral Zinreich score in at least 1 pair of the anterior ethmoid, maxillary, posterior ethmoid, frontal, or sphenoid sinuses in CSsNP and CSwNP subjects at Week 24
 
- CFBL in bilateral Zinreich scores of posterior ethmoid, frontal, sphenoid, maxillary, anterior ethmoid sinus, and OMC pairs in CSsNP and CSwNP subjects at Week 24
 
- CFBL in total Zinreich score at in CSsNP and CSwNP subjects at Week 24
 

To assess effect of LYR-210 in improving smell function in CSsNP and CSwNP subjects
	
 
- CFBL in UPSIT score in CSsNP and CSwNP subjects at Week 24
 

To assess the safety of subjects post LYR-210 treatment
	
 
- Severity and percentage of subjects reporting AEs and SAEs through Week 28 and Week 48
 
- Percentage of subjects with abnormal and clinically significant abnormal laboratory values (hematology and chemistry, vital signs) at Week 28
 
- Morning serum cortisol levels at Week 28
 
- Plasma MF concentrations at Week 28
 

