#### **10.6.2.2 Percentage of Subjects with Improved bilateral Zinreich score**

The second key secondary endpoint is the percentage of subjects with at least 1-point decrease in bilateral Zinreich score in at least one pair of the anterior ethmoid, maxillary, posterior ethmoid, frontal, or sphenoid sinuses post treatment. Treatment groups will be compared using logistic regression adjusting for the baseline total Zinreich score and randomization strata. This analysis will be performed using subjects in the ITT analysis set with available post-treatment MRI data and repeated with the PP analysis set. There will be no imputation of missing data.

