15.2. SECONDARY EFFICACY

15.2.1. KEY SECONDARY EFFICACY ENDPOINTS AND DERIVATION

15.2.1.1. CFBL in CS7DA4S at Week 24

CFBL at Week 24 will be derived as described in Section 15.1.1.

15.2.1.2. Proportion of Subjects with at Least 1-point Decrease in Bilateral Zinreich Score in at Least One Pair of Anterior Ethmoid, Maxillary, Posterior Ethmoid, Frontal or Sphenoid Sinuses at Week 24

Sinus inflammation will be assessed by MRI at time points specified in the schedule of events in Section 8.1 of the protocol. The sinus inflammation will be assessed using the Zinreich modified Lund-Mackay scoring system (Likness, et al., 2014). The Zinreich score for each sinus will be assessed by Medical Metrics, Inc. (MMI) and all analysis will use the data collected by MMI. Six areas of each sinus (left and right) will be assessed:

- Anterior ethmoid
- Maxillary
- Posterior Ethmoid
- Frontal
- Sphenoid
- Ostiomeatal Complex (OMC)

Each area will be assigned a score based on the percentage of opacification as follows:

- 0=0%
- 1=1%-25%
- 2=26%-50%
- 3=51% to 75%
- 4=76% to 99%
- 5=100% or completely occluded

The OMC is given a score of 0 to 2 as follows:

- 0=completely patent
- 1=partially occluded
- 2=completely occluded

The bilateral Zinreich score for each area will be derived by [REDACTED] Biostatistics by adding the score for both sinuses together. The range of the score will be 0-10 except for OMC which will have a range of 0-4. The bilateral Zinreich score for each area will only be calculated if both sinus scores are non-missing. The total bilateral score

will be the sum of all 6 areas and will have a range of 0-54. The total bilateral score will only be calculated when all bilateral scores for each of the 6 areas are present. The baseline bilateral Zinreich score for each area and baseline total score will be the value recorded at screening. The individual and total Zinreich scores for all areas at all visits will be summarized and listed.

The key secondary endpoint will be the proportion of subjects with at least 1-point decrease from baseline in the Zinreich score in at least 1 pair of the anterior ethmoid, maxillary, posterior ethmoid, frontal or sphenoid sinuses at Week 24.

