15.3.1.3. CFBL in Endpoints by Absence or Presence of Nasal Polyps

The secondary endpoints analysis will be repeated using the subgroups of subjects without nasal polyps (CSsNP), and subjects with nasal polyps (CSwNP). The endpoints to be summarized by these subgroups are:

- CFBL in CS7DA4S score at Weeks 1, 2, 3, 4, 8, 12, 16, 20 and 24

- CFBL in 7-day average score of individual cardinal CS symptoms at Weeks 1, 2, 3, 4, 8, 12, 16, 20 and 24
- CFBL in SNOT-22 domain and total scores at Weeks 2, 4, 8, 12, 16, 20 and 24
- CFBL in SF-36 domain and overall component summary measure scores at Week 24
- Percentage of subjects with at least 1-point decrease in any area for the bilateral Zinreich score at Week 24
- CFBL in each of the 5 bilateral Zinreich sinus scores, Zinreich OMC score and Zinreich total score at Week 24
- CFBL in USPIT™ total olfaction score at Week 24

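### The MRI responder is defined on three, five or six areas in different places, so the key secondary endpoint and its polyp-subgroup repeats do not share one rule

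*Protocol*

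**What the plan says.** **Polyp-subgroup responder (exploratory, Week 24)**

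- Protocol Section 3, exploratory objectives: three pairs, "in at least 1 pair of the posterior ethmoid, frontal, or sphenoid sinuses in CSsNP and CSwNP subjects at Week 24".
- Protocol synopsis, same endpoint and subgroups: five pairs, "in at least 1 pair of the anterior ethmoid, maxillary, posterior ethmoid, frontal, or sphenoid sinuses in CSsNP and CSwNP subjects at Week 24".
- SAP 15.3.1.3: "Percentage of subjects with at least 1-point decrease in any area for the bilateral Zinreich score at Week 24". SAP 15.2.1.2 sets out what an area is: "Six areas of each sinus (left and right) will be assessed". It lists the five sinuses and the OMC.

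**Overall responder (key secondary, Week 24)**

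- Protocol Section 3: five pairs, "in at least 1 pair of the anterior ethmoid, maxillary, posterior ethmoid, frontal, or sphenoid sinuses at Week 24".
- Protocol 10.6.2 gives the same five, as does 10.6.2.2: "in at least one pair of the anterior ethmoid, maxillary, posterior ethmoid, frontal, or sphenoid sinuses post treatment".
- SAP 15.2.1.2 (definition): five pairs, "in at least 1 pair of the anterior ethmoid, maxillary, posterior ethmoid, frontal or sphenoid sinuses at Week 24".
- SAP 15.2.4.2 (analysis): counts subjects improving in one of six bilateral scores, citing 15.2.1.2, and sets the responder indicator to 1 for a 1-point decrease in any score.

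SAP 3.3, which lists departures from the protocol, mentions none of these differences.

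**The concern.** Nasal polyp status is a randomization stratum, and SAP 15.3.1.3 presents the subgroup analysis as a repeat of the secondary analysis. The natural use of the subgroup rows is to see whether the overall MRI result holds with and without polyps. That only works if a subject has the same responder status in both tables.

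As written, status can change with the table. Protocol Section 3 narrows the rule in the strata, whereas the SAP's analysis and subgroup wording widens it. Because SAP 15.2.4.2 departs from the five-pair definition it cites, the ambiguity also reaches a key secondary endpoint. A programmer could follow any of these texts in good faith and get different counts from the same MRI scores.

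**Working it through.** The plan states no figure for this point, so there is nothing to reproduce. The check compares the definitions, counts the affected patterns, and then illustrates size under stated assumptions.

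**1. Does six include the OMC?** Yes. Later in SAP 15.2.4.2, and in the bullet after the responder bullet in 15.3.1.3, the SAP counts five sinus scores and names the OMC score separately. Five plus the OMC is the only route to six.

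**2. Patterns, no distributional assumption.** Mark each pair as improved by at least 1 point or not.

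- Five pairs give 2^5 = 32 patterns. Five-pair responders: 32 − 1 = 31. Three-pair responders: 32 − 2^2 = 28. Difference: 31 − 28 = 3 patterns, namely anterior ethmoid only, maxillary only, or both.
- Six areas give 2^6 = 64 patterns. Any-area responders: 64 − 1 = 63. Five-pair responders: 64 − 2 = 62. Difference: 1 pattern, OMC only.
- With five pairs used both overall and in the strata, 0 of 32 patterns are classified differently.

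The rules are nested: three-pair responders are a subset of five-pair responders, who are a subset of any-area responders. Within any one group of subjects the rates must follow that order.

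**3. Size with independent areas.** Assume each area has the same chance q of improving (q is not in the documents). The responder rate on k areas is 1 − (1 − q)^k.

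| q | 3 pairs | 5 pairs | 6 areas | 5 minus 3 | 6 minus 5 |
|---|---|---|---|---|---|
| 0.1 | 27.1% | 41.0% | 46.9% | 13.9 | 5.9 |
| 0.2 | 48.8% | 67.2% | 73.8% | 18.4 | 6.6 |
| 0.3 | 65.7% | 83.2% | 88.2% | 17.5 | 5.0 |
| 0.5 | 87.5% | 96.9% | 98.4% | 9.4 | 1.6 |

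For q = 0.2: 1 − 0.8^3 = 0.488 and 1 − 0.8^5 = 0.672.

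**4. Size with correlated pairs.** Simulate 400,000 subjects with normal pair changes rounded to whole points. A responder has at least one change of −1 or lower. Means, SDs and correlations are all assumed.

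| Mean change | SD | Correlation | 3 pairs | 5 pairs | Gap |
|---|---|---|---|---|---|
| 0 | 0.6 | 0.3 | 43% | 56% | about 13 |
| 0 | 0.8 | 0.3 | 53% | 67% | about 13 |
| 0 | 1.0 | 0.3 | 59% | 72% | about 13 |
| −1 | 0.8 | 0.3 | 95% | 98% | about 3 |

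With no mean change and SD 0.6 to 1.0, the gap is about 17 to 19 points at correlation 0 and 8 to 9 points at correlation 0.6. Across everything examined, it runs from roughly 3 to 19 points.

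**5. Must both strata fall below the overall rate?** No. Take two equal strata, SD 0.8, correlation 0.3, and mean changes of −0.6 and 0. The three-pair rates are 84% and 53%, against a five-pair overall rate of 79%. The average of the strata, (84 + 53)/2 = 68.5%, lies below 79%, but the first stratum lies above it.

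**The case against.** The strongest reply is that the SAP governs the analysis and contains no three-pair rule. SAP 15.3.1.3 repeats the secondary analysis. SAP 15.3.3 handles dichotomous exploratory endpoints like the key secondary and restates its five pairs. SAP 15.2.4.2 points back to the five-pair definition. On that view five pairs are clearly intended and the rest is loose wording. This stands as evidence of intent, but it neither amends Protocol Section 3 nor removes the six-score and any-area wording.

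It does limit the consequence. A reader might infer that the SAP, too, makes a subject a responder overall and a non-responder in the stratum. It does not: any area is at least as wide as five pairs, so an OMC-only improver is the one who differs from the five-pair definition, and in the opposite direction. The overall-yes, stratum-no result comes from Protocol Section 3 alone.

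A reader might also take 13 points as the expected gap. It depends on assumed SDs, a correlation of 0.3 and no true change, and treats the pairs as interchangeable with no floor at zero. MRI exclusion 6a requires a bilateral score of at least 4 in at least one of the three narrower pairs, so those pairs are not typical of the five. The narrower rule also applies to all arms, so no bias in the dose-versus-sham comparison has been shown.

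Finally, the subgroup endpoint is exploratory with nominal p-values, about 70 subjects are divided over three arms and two strata, and SAP 7.6 concedes low subgroup power. All of this stands and bounds the importance of the point.

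**Conclusion.** The inconsistency is real and lies in current text. One responder concept has three definitions, they classify some subjects differently, and SAP 3.3 is silent. Of the 32 five-pair patterns, 3 change status between the overall and stratum rules of Protocol Section 3. Of the 64 six-area patterns, 1 changes between the five-pair definition and the SAP's wider wording. These counts need no assumptions, but they are counts of patterns, not proportions of subjects.

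The direction is also certain: a stratum's three-pair rate cannot exceed its own five-pair rate. The size is not known. The range of roughly 3 to 19 points reflects chosen means, SDs, correlations and improvement chances that the documents do not give. It may be tempting to conclude that both strata must fall below the overall rate; the documents do not support this, because only their weighted average is bounded by it.

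The most consequential place is SAP 15.2.4.2, because it concerns a key secondary endpoint. The primary analysis and the sample size are unaffected.

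**What to change.** Before unblinding, state the same five-pair list (anterior ethmoid, maxillary, posterior ethmoid, frontal and sphenoid, with the OMC explicitly excluded) in three places:

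1. Protocol Section 3, exploratory polyp-subgroup responder, replacing the three-pair list.
2. SAP 15.2.4.2, replacing both the reference to six scores and the reference to any score.
3. SAP 15.3.1.3, replacing the reference to any area.

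All three are needed. If 15.2.4.2 were left on six scores, five-pair subgroup rows would still not break down the key secondary result. If a different rule is intended anywhere, declare it in SAP 3.3 with a reason.

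The cost is three wording corrections and a check of the responder flag in the programs. Every area is already scored on each MRI, so no new data are needed.
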